1.1 Background

One important approach for decreasing COVID-19 transmission in healthcare settings is to prevent healthcare professionals from working while ill. Currently, facilities are asking screening questions and measuring temperatures to help identify symptomatic healthcare professionals and exclude them from providing patient care. Simulations can be used to inform the effectiveness of different screening approaches, but the results of these simulations depend upon the effectiveness of the intervention, e.g., the ability to identify healthcare professionals on their way to work, or to study the impact of healthcare professionals returning to work too early. Thus, simulations must necessarily depend upon realistic disease parameters: for example, it is suspected that a non-trivial proportion of patients with COVID-19 may be asymptomatic or have minimal symptoms, but the relative size of the asymptomatic subpopulation is unknown.

The plan for this study is to develop a method for granular measurement of twice-daily symptoms from healthcare professionals and other research subjects of similar ages. After being diagnosed, the goal is to determine what symptoms participants have and how long they have had them. This will be done using a previously developed bidirectional texting platform to query participants about symptoms at least twice a day for ten days post diagnosis. Participants will be asked about subjective symptoms, including fevers, chills, cough, shortness of breath, fatigue, gastrointestinal symptoms, etc. They will also take their temperature twice daily during the recovery period, which will help determine the effectiveness of screening based on symptoms and/or thermometer readings.

2. Objective and Aim

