3.1 Inclusion Criteria

- Age 18 – 100 years
- Able to speak and read English
- Have tested positive for COVID-19

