3.3 Exclusion Criteria

- prisoner status
- unable to provide own written informed consent

4. Study Design

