4.3 Visit Procedures

We will collect the following data from the patient's medical record: date of birth, date of COVID test, type of COVID test, and COVID test number.

Immediately after the participant completes the online REDCap consent form, they will be

directed to the baseline survey. The baseline survey asks for the participant's cell phone number so that we can send them the twice daily survey, the time in the morning they wish to receive text messages, the time in the evening they wish to receive text messages, their mailing address for the compensation check, sex assigned at birth, if they are pregnant (if female), race, ethnicity, if they have any of a list of health conditions that have been shown to be related to worse COVID outcomes, if they are a smoker, and if they have a thermometer that they are able to use for the study. If they do not have a thermometer, we will drop one off outside their home so that they have one to use for the study.

Once that is complete, they will be entered into our bi-directional text messaging platform and sent 1 message every morning and 1 message every evening. These messages will remind them to measure their temperature and will ask about any current COVID-19 symptoms that they are experiencing. They will be sent text message reminders for 10 days.

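### The baseline survey does not record which queried symptoms were usual before COVID-19, so long-standing cough, breathlessness, fatigue or gastrointestinal symptoms may be counted as COVID-19 symptoms, to an unknown degree

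*Combined protocol and SAP*

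**What the plan says.** Section 4.3 lists what is collected at entry. The medical record supplies four items: "date of birth, date of COVID test, type of COVID test, and COVID test number". The baseline survey covers contact and timing details, sex, pregnancy, race, ethnicity, possession of a thermometer, and, on health, "if they have any of a list of health conditions that have been shown to be related to worse COVID outcomes, if they are a" (smoking status follows). No item concerns symptoms that were present before the infection, or when a symptom began.

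Eligibility is wide. Section 3.1 admits "Age 18 – 100 years". Section 3.3 excludes only prisoners and people "unable to provide own written informed consent". Nothing excludes smokers or people with chronic disease, and the baseline questions show that the plan expects them.

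Section 1.1 describes the queries as covering "subjective symptoms, including fevers, chills, cough, shortness of breath, fatigue, gastrointestinal symptoms, etc", and section 4.3 says that the twice-daily messages "will ask about any current COVID-19 symptoms that they are experiencing". The messages run for 10 days, so at most 20 per participant. Section 1.1 also says that "the goal is to determine what symptoms participants have and how long they have had them", but no item in 4.3 asks for this.

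Section 4.1 describes a single observational cohort. Section 4.4 plans to describe which symptoms occur and their duration. It gives no rule for symptoms that pre-date the infection and uses comorbidity only as a summary count.

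**The concern.** Apart from fever and chills, the named symptoms are ordinary complaints in smokers and in people with chronic disease. A person who coughs every day has no onset or resolution of that cough within this infection. If the cough is reported, it enters the results as a symptom present at every text and still present at the last. If the person judges it not to be a COVID-19 symptom and leaves it out, a genuine worsening may be left out too. The two errors run in opposite directions, and nothing in the planned data tells them apart.

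The quantities exposed are the prevalence and duration of the non-fever symptoms and the share still symptomatic at the end of follow-up. The count of symptom-free participants is exposed as well. Section 1.1 wants realistic parameters for simulations and calls the size of the asymptomatic group unknown; a participant with no COVID-19 symptoms who reports a usual cough would be classed as symptomatic.

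**Working it through.** **The omission.** I compared every baseline and record item in 4.3 with the information needed to separate a usual symptom from a new one. The comorbidity and smoking items identify people in whom a usual symptom is more likely, but not whether a given person has one, or which. With no comparison group, the background rate cannot be estimated from elsewhere in the study.

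**Is there a plan figure to reproduce?** The only design figure is the enrolment of 500. Section 4.4 says that it was set without a power analysis, and it does not bear on this point.

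**Possible size.** The documents give no prevalence for usual symptoms, so all inputs except 500 are assumptions:

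- t: true share with the COVID-19 symptom on day 10
- c: share with the same symptom as their usual state, independent of t
- r: probability that such a person reports the usual symptom when asked about current COVID-19 symptoms
- all 500 followed to day 10

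Reported day-10 share = t + (1 − t) × c × r.

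With t = 5% and c = 10%:

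- r = 0: 5%, or 25 of 500
- r = 0.5: 5% + 0.95 × 10% × 0.5 = 9.75%
- r = 1: 5% + 0.95 × 10% = 14.5%, or 72.5 of 500

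Varying c at t = 5%:

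| c | r = 0 | r = 0.5 | r = 1 |
|---|---|---|---|
| 5% | 5% | 7.4% | 9.75% |
| 10% | 5% | 9.75% | 14.5% |
| 20% | 5% | 14.5% | 24% |

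**The opposite error.** If all those with the usual symptom (c = 10%, 50 people) also leave out a real worsening, only the other 450 contribute: 450 × 5% / 500 = 4.5% against a true 5%.

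**Prevalence and duration.** Assume also that the true symptom occurs in 50%, lasts 5 days on average, and persists to day 10 in 10% of those affected (50% × 10% = 5%, matching t). With c = 10%, and usual symptoms counted as lasting all 10 days:

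- r = 1: reporters 450 × 0.5 + 50 = 275 (55%); mean duration (225 × 5 + 50 × 10) / 275 = 5.9 days
- r = 0.5: reporters 475 × 0.5 + 25 = 262.5 (52.5%); mean duration (237.5 × 5 + 25 × 10) / 262.5 = 5.5 days
- r = 0: 50% and 5.0 days

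**Against sampling error.** At t = 5% and N = 500 the 95% half-width is 1.96 × √(0.05 × 0.95 / 500) = 1.9 points. The bias exceeds it once c × r passes 0.019 / 0.95, about 2%. At t = 20% the half-width is 3.5 points and the threshold is 0.035 / 0.80, about 4.4%. Enrolling more people would not reduce the bias.

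**What a baseline item would recover.** Restricted to people without the usual symptom, the day-10 share at c = 10% is 22.5 / 450 = 5%, whatever the value of r. This assumes accurate recall.

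**The case against.** The strongest reply is that the texts ask about current COVID-19 symptoms, and 4.1 likewise speaks of symptoms with the infection. That framing invites participants to leave out a usual cough, and if they all do, the excess is zero. The item wording is not in the documents, so it may already include a suitable instruction. This stands: a reader might infer that usual symptoms *are* counted as COVID-19 symptoms, but the documents support only that they *may* be. The framing does not close the gap, because it leaves attribution to each ill participant and records nothing that would let the analyst check it.

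Other parts of the reply also stand:

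- The 14.5% figure is the top of a range that starts at no excess, and it assumes complete follow-up, whereas 4.4 expects many dropouts.
- Fever timing and duration, the leading examples in 4.4, rest largely on measured temperature and are little affected.
- A constant background of 10% would shrink absolute day-to-day and morning-to-evening changes by only about 10% and would not move the peak, so a serious flattening of the time course should not be inferred.
- A reader might also infer that differences by comorbidity would be artefacts. Section 4.4 plans no such comparison.

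It can also be said that this is a descriptive pilot, that smoking and comorbidity are recorded, and that identical answers at every text would be visible. Such summaries are possible, but none is planned, and none would show that a symptom pre-dated the infection. Describing symptoms is the whole purpose of the study, so the descriptive label does not remove the point.

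**Conclusion.** The point holds in a limited form. The omission can be verified in 4.3, and the eligible population and single-cohort design make it relevant. Long-standing cough, breathlessness, fatigue or gastrointestinal symptoms may be counted as COVID-19 symptoms persisting to the last text, and the planned data cannot show how often.

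The size is unknown. With a usual-symptom share of 5% to 20% and a true day-10 share of 5%, the excess runs from nothing to 19 points, governed mainly by how many people report their usual symptoms, which the documents do not indicate. Modest reporting would be enough to outweigh sampling error: a 10% usual share with one in five reporting already reaches the 2% threshold. These figures rest on assumed inputs, independence and full follow-up; they show scale and are not estimates.

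This is a cheap improvement to what the study can conclude. It does not invalidate the design or change the target of 500.

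**What to change.** Add one tick-list to the REDCap baseline survey, using the same symptoms as the texts: *In a usual week before this illness, did you have this?* Leave the text items unchanged. Rewording them to ask only for symptoms that are new or worse than usual would lose the any-symptom data, and would still leave the judgement to the participant.

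In 4.4, state that each symptom's prevalence, time course and duration will be reported for all participants and, beside it, for participants who did not usually have that symptom before COVID-19. The restriction is made symptom by symptom, so a usual cough does not remove a person from the fatigue results.

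The cost is about a minute more at baseline, some recall error, and a smaller denominator in the second set of figures (450 of 500 if 10% usually have the symptom, 400 if 20% do, before dropout). The second set describes people without the usual symptom; it does not measure worsening in those who have it, and the report should say so. The item belongs at baseline, since none of the listed record items can supply it later.

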4.4 Statistical Analysis Plan

We will calculate summary statistics for participants' demographic characteristics (e.g., mean age, counts of comorbidities, percentage of females). We will also determine the progression of temperatures and symptoms over time. For example, we will determine when fevers occur, how many days fevers last, what symptoms are present, and how long symptoms last.

This is a descriptive pilot study, so no power analysis was performed or required. 500 was chosen as the number to enroll because we need a large sample of participants to learn about the various symptoms of this condition. Also, due to the remote nature of the study and the fact that the population is already known to be ill, we expect a large number of dropouts during the course of the study.

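### The baseline survey lists no symptom or temperature item, so participants who never answer a text have no outcome record and cannot be compared with repliers on illness at entry

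*Combined protocol and SAP*

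**What the plan says.** Section 4.3 describes three sources of data.

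- **Medical record:** "date of birth, date of COVID test, type of COVID test, and COVID test number".
- **Baseline survey**, reached directly after electronic consent: phone number, preferred text times, mailing address, "sex assigned at birth, if they are pregnant (if female), race, ethnicity", a list of health conditions linked to worse COVID outcomes, and finally "if they are a smoker, and if they have a thermometer that they are able to use for the study".
- **Text messages**, one each morning and one each evening for 10 days, starting only after the baseline survey is complete. They prompt a temperature measurement and "will ask about any current COVID-19 symptoms that they are experiencing".

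Section 4.4 plans summaries of demographics and of the course of temperatures and symptoms, including which symptoms are present and how long they last. On sample size it says "500 was chosen as the number to enroll because we need a large sample of participants", and on attrition "we expect a large number of dropouts during the course of the study". It gives the remote setting and the participants' illness as reasons, and no rate. It describes no comparison of those who reply with those who do not, and no handling of missed replies.

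**The concern.** Symptoms and temperature are the study's outcomes, yet none is listed for collection at the one point where a participant is already filling in a study form about their health. Every outcome value depends on a later text reply. Section 4.4 itself connects dropout partly with being ill. If the people who never start replying are sicker, or less sick, than those who do, the symptom picture at entry describes the repliers only. Any adjustment for missed replies would have to rest on demographics, health history and test data, which may not capture how ill a person was on that day.

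This touches the study's purpose. Section 1.1 wants realistic disease parameters for simulation, and gives the unknown size of the asymptomatic group as its example. The share of participants with symptoms at entry bears on that quantity.

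**Working it through.** **Reading check.** I set the items in section 4.3 against what each group of participants would have on file.

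| Data | Never-replier | Replier |
|---|---|---|
| Age, test date, test type | yes | yes |
| Sex, pregnancy, race, ethnicity | yes | yes |
| Health conditions, smoking, thermometer access | yes | yes |
| Any symptom or temperature | none described | from texts |

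The screening questions in section 4.2 are only linked, so a symptom item there cannot be ruled out. Their stated purpose is eligibility, and no criterion in sections 3.1 or 3.3 concerns symptoms.

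**The plan's own figure.** The 500 in section 4.4 has no formula, precision target or dropout rate behind it, so there is nothing to reproduce. No stated figure is contradicted.

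**Illustration of size.** Inputs: N = 500 (section 4.4), taken as all having completed the baseline survey; never-reply share r = 5%, 10%, 20%, 30% (assumed); symptomatic share among repliers p = 60% (assumed).

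- Lower bound, no never-replier symptomatic: p(1 − r).
- Upper bound, all never-repliers symptomatic: p(1 − r) + r.
- The width is therefore r. Example at r = 20%: 0.60 × 0.80 = 0.48, and 0.48 + 0.20 = 0.68.
- Full width of the 95% sampling interval among the n = 500(1 − r) repliers: 2 × 1.96 × √(0.60 × 0.40 / n). Example at n = 400: 3.92 × √0.0006 = 0.096.
- Smallest difference between never-repliers (m) and repliers (n) detectable on a yes/no item at two-sided 5% and 80% power, taking 50% prevalence as the least favourable case: (1.96 + 0.84) × √[0.25(1/n + 1/m)].

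| r | Never reply / reply | Bounds for all 500 | Width (points) | Sampling interval width (points) | Detectable difference (points) |
|---|---|---|---|---|---|
| 5% | 25 / 475 | 57–62% | 5 | 8.8 | 28.7 |
| 10% | 50 / 450 | 54–64% | 10 | 9.1 | 20.9 |
| 20% | 100 / 400 | 48–68% | 20 | 9.6 | 15.7 |
| 30% | 150 / 350 | 42–72% | 30 | 10.3 | 13.7 |

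At an assumed 5% the sampling error is the larger uncertainty. At about 10% the two are similar, and beyond that the missing outcomes dominate. A larger enrolment does not narrow the bounds, because their width depends on r and not on N.

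**Effect of the fix.** If a share a of never-repliers answers the new baseline symptom item, the width falls from r to r(1 − a). It reaches zero only if all of them answer. For temperature it cannot be assumed to reach zero, because some participants have no thermometer until one is delivered (section 4.3).

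**The case against.** A reader might infer that never-repliers cannot be compared with repliers at all. The documents do not support that: the record extract and the baseline survey give age, sex, pregnancy, race, ethnicity, health conditions, smoking, thermometer access and test data without any text reply. Only illness at entry is out of reach, although section 4.4 describes no comparison even on the variables that are held.

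A reader might also equate the expected dropouts with never-repliers. Section 4.4 speaks of dropouts over the course of the study. Anyone who answers even one text has an early symptom record, so later dropouts can already be compared with continuing repliers on first replies. The gap is limited to people who complete consent and the survey and then answer none of 20 prompts (2 a day for 10 days). Nothing says this group is large.

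The attribution of dropout to illness is partial, since section 4.4 also cites the remote setting. That illness is the main driver of dropout is not established.

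Finally, the plan says "This is a descriptive pilot study, so no power analysis was performed or required", and its aims concern duration, progression and time of day. One record at entry adds little to those for a never-replier, and it does not reach people who ignore the recruitment emails.

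All of this stands and narrows the point. It does not remove it: which symptoms are present is among the planned summaries, and an entry measure is the direct way to see whether early loss is related to illness.

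**Conclusion.** The point holds in a limited form. As listed, the baseline survey leaves never-repliers without any symptom or temperature record, so a possible illness-related bias in the entry symptom profile could not be seen directly in the data held on them. The size is unknown. The bounds above rest on an assumed prevalence and assumed never-reply shares, and they are worst-case limits, not estimates of bias. The documents do not show that such bias will occur, and they do not support the inference that the two groups cannot be compared on anything. This is a cheap improvement to a descriptive study and worth making; it is not an error that invalidates the plan.

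**What to change.** - **Section 4.3:** add to the baseline survey the same symptom checklist that the texts use, with a temperature reading where a thermometer is already at hand.
- **Section 4.4:** report entry symptoms on all who complete the baseline survey, with the number who left the item blank. Compare entry symptoms, and the baseline variables already held, between never-repliers or early dropouts and continuing repliers. Use entry symptoms as a predictor in any adjustment for missed replies.

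**Cost:** a small change to an existing REDCap form and about a minute more per participant (an estimate), with no added staff or procedure.

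**Limits:** the baseline record does not fall in a morning or evening slot, so it should stay out of the time-of-day summary. It gives no duration or progression for never-repliers. It narrows the bounds only as far as participants answer the new items. With few never-repliers, the comparison would detect only large differences, so report it with confidence intervals and do not read a non-significant result as absence of bias.

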2.1 Objective

The goal of this trial is to further the understanding of COVID-19 symptom development throughout the infection period, as well as how those symptoms vary at different points of the day.

3. Subject Inclusion/Exclusion Criteria

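### Section 4.3 lists no item on symptom onset or on symptoms before enrolment, so an episode that began before the first text has at best a lower-bound duration

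*Combined protocol and SAP*

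**What the plan says.** Section 2.1 gives the aim as "to further the understanding of COVID-19 symptom development throughout the infection period". Section 4.4 promises specific outputs: "we will determine when fevers occur, how many days fevers last, what symptoms are present, and how long symptoms last". Section 1.1 adds an aim that reaches back before enrolment: "After being diagnosed, the goal is to determine what symptoms participants have and how long they have had them". It also names the tool: "This will be done using a previously developed bidirectional texting platform to query participants about symptoms".

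Section 4.3 describes three sources of data:

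- **Medical record:** "date of birth, date of COVID test, type of COVID test, and COVID test number".
- **Baseline survey:** phone number, preferred morning and evening text times, mailing address, sex, pregnancy, race, ethnicity, health conditions, smoking and access to a thermometer.
- **Texts:** one each morning and one each evening, which prompt a temperature reading and "will ask about any current COVID-19 symptoms that they are experiencing". On follow-up, the section says: "They will be sent text message reminders for 10 days".

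Section 4.2 also mentions screening questions, described as serving to establish eligibility. Neither that form nor the wording of the texts is reproduced.

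**The concern.** Every participant enters after a positive test, and the first text comes later still. Symptoms that began before that text are therefore foreseeable. For those episodes the start date is needed for both timing and duration, and no listed item supplies it. Section 1.1 expects the texting platform to show how long symptoms have been present, but the description of the texts in 4.3 contains nothing that would deliver this.

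Two different losses follow. An episode still present at the first text is seen only from that text onward. An episode that ended before it is not seen at all, and that participant cannot be told apart from someone who never had the symptom. Section 4.4 has no rule for either case. A reader could take a summary of observed days as the duration of illness, when it is the part of the illness that happened to fall after enrolment.

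**Working it through.** The plan gives no figure to reproduce: 4.4 states that no power analysis was done, and no duration or lag appears anywhere. The check is of the listed items, followed by the censoring logic and one illustration.

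**1. Item check (4.3).**

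| Source | Items listed | Items on onset or past symptoms |
|---|---|---|
| Medical record | 4 | 0 |
| Baseline survey | 11 (counting the two text times separately) | 0 |
| Texts | temperature prompt; current symptoms | 0 |

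The test date gives a time axis, but it is not the date of onset.

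**2. Is the lag from onset to first text limited?** Section 3.1 sets no maximum time since the positive test. Section 4.2 allows a second email with no stated interval. Section 4.3 counts its 10 days of texts from entry to the platform. Section 1.1 does speak of querying over the ten days after diagnosis. Read literally, that would limit the gap from test to text, but 3.1, 4.2 and 4.3 do not enforce it. It would not limit the gap from onset to text in any case.

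**3. What is recorded.** Put onset at time 0, true duration D, and first text at L > 0. With 10 days of texts and no start date,

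- if D > L, the recorded part is min(D, L + 10) − L;
- if D ≤ L, nothing is recorded.

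Example, with D and L assumed:

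| True duration D | L = 2 days | L = 4 days | L = 6 days |
|---|---|---|---|
| 8 days | 8 − 2 = 6 recorded | 8 − 4 = 4 recorded | 8 − 6 = 2 recorded |
| 3 days | 3 − 2 = 1 recorded | none | none |

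Each recorded value is a lower bound, short by L.

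**4. Share of episodes missed altogether.** The documents give neither lags nor durations, so all inputs here are assumptions: fever duration lognormal with log-SD 0.6, lag gamma with shape 4 and mean 2 days, and every fever counted began before the first text. The share already over is P(D < L) = ∫ F_D(t) f_L(t) dt. Numerical integration gives:

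| Median fever duration | Already over at first text |
|---|---|
| 3 days | 0.255 |
| 4 days | 0.151 |
| 5 days | 0.092 |

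That is 9-25% of fevers that began before the first text, not of all fevers. Other assumptions give other answers. For example, exponential durations with mean 4 days and a mean lag of 1 day give about 21%.

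**5. Direction of bias in a mean.** Compare the mean of D − L among episodes with D > L with the mean of all D, setting aside the 10-day limit so that only late entry acts:

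- exponential, mean 4: 4.00 against 4.00, no bias;
- lognormal, median 3, log-SD 1.0, mean lag 1: 4.66 against 4.95, about 6% low;
- the same durations, mean lag 5: 5.69 against 4.95, about 15% high.

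Each observed episode is shortened, but short episodes also drop out and long ones remain. The net effect on a cohort mean can go either way.

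**The case against.** The strongest reply is that the instruments are not in the documents and that 1.1 gives this very task to the texting platform. The texts may ask since when a symptom has been present, and 4.3 does not say that they ask about current symptoms and nothing else. This stands in part. The finding is about what 4.3 lists, and the lower-bound statement holds only if no instrument asks for a start date. The reply is weaker for symptoms already over: 1.1 speaks of the symptoms participants have, and a since-when question about a current symptom would not reach one that has ended.

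A second reply is that this is a descriptive pilot. But timing and duration are the descriptive outputs it promises, and enrolling 500 people does not recover a variable that was not collected.

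Three stronger readings are tempting and are not supported:

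- *Mean durations will be underestimated.* Step 5 shows cases with no bias and with upward bias. The 10-day limit on texting does shorten recorded durations, but that is a separate matter from missing onset.
- *The study will misestimate the asymptomatic share.* Section 1.1 says "the relative size of the asymptomatic subpopulation is unknown" as an example of what simulations need. Neither 2.1 nor 4.4 plans to estimate it.
- *The remark in 4.4 that participants are already ill shows a long lag.* That remark explains expected dropout and says nothing about elapsed time.

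**Conclusion.** The concern holds, as a gap between the aims in 1.1, 2.1 and 4.4 and the items listed in 4.3. If 4.3 is followed as listed, timing and full duration cannot be obtained for episodes that began before the first text, and episodes already over are invisible. Confidence is high for the listing gap and does not extend to any effect size. The 9-25% figure rests wholly on the assumed durations and lags and shows only that the loss need not be trivial. Episodes that start within the 10 days, and morning/evening variation, which is the other half of the objective, are not touched. This should be fixed, and the improvement is cheap. It does not invalidate the study.

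**What to change.** **Section 4.3.** Add to the baseline REDCap survey:

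- whether any COVID-19 symptom has occurred so far;
- the date of the first symptom;
- the same symptom checklist as the texts, fever included, with start date, whether still present, and end date if not.

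If the screening form or the texts already ask this, list it in 4.3 instead.

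**Section 4.4.**

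- Report progression by days since onset for participants with symptoms, alongside days since test for everyone.
- Report durations separately for episodes that began before and after the first text.
- Keep recalled fever separate from fever measured by thermometer.
- Call a participant symptom-free only if both the baseline history and the answered texts are free of symptoms.

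If no onset item is added, label every duration as *observed from first text*.

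**Cost.** A few more questions in an online survey that participants already complete, plus a few sentences in 4.4. The downsides are recall error in the dates, fever before enrolment that was never measured, and a slightly longer survey. The questions are best in place before enrolment, because the listed data cannot supply onset afterwards.

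### The fixed 10-day texting window right-censors fever and symptom duration for anyone still symptomatic at the last text, and its start date is not settled

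*Combined protocol and SAP*

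**What the plan says.** Section 4.3 has each participant "sent 1 message every morning and 1 message every evening", and then sets the length: "They will be sent text message reminders for 10 days". That is at most 2 × 10 = 20 prompts. The length does not depend on symptom state, and no section describes a later contact or a question on when symptoms ended.

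The objective in section 2.1, repeated in section 4.1, is to "further the understanding of COVID-19 symptom development throughout the infection period". Section 4.4 plans to determine "how many days fevers last, what symptoms are present, and how long symptoms last". It names no method for episodes still open when texting ends.

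On the start of the window, section 1.1 plans to "query participants about symptoms at least twice a day for ten days post diagnosis". Section 4.3 instead begins texting after consent and the baseline survey: "Once that is complete, they will be entered into our bi-directional text messaging platform".

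Two further phrases in section 1.1 bear on the late illness. One concerns temperatures: "They will also take their temperature twice daily during the recovery period". The other, given as an example of what simulations can be used for, reads "or to study the impact of healthcare professionals returning to work too early".

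**The concern.** A duration is observed only if its end is observed. A participant who still reports a symptom or fever at the last text contributes only a lower bound. The study then has no record of resolution in that person, although resolution is part of both the objective and the planned duration summaries.

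Two problems follow, and they need different remedies. The first is analytical. If the last text is treated as recovery, or unresolved participants are left out, average duration is understated; a censoring method avoids that. The second is one of data collection. No method shows what happens after the last text, and if half or more of participants still have a given symptom then, its median duration cannot be estimated without extrapolation.

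The unsettled start date adds to this, because it decides which part of the illness the ten days cover and how many days of texting a late enroller receives.

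**Working it through.** **Inputs from the documents.** Window 10 days (sections 1.1 and 4.3); two prompts a day (4.3); planned enrolment 500, not derived from a formula (4.4); many dropouts expected, with no figure (4.4). There is no duration figure, power calculation or alpha to reproduce.

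**Assumed inputs.** Median time *m* from first text to resolution of 5, 7, 10 or 14 days; three distribution shapes; no dropout.

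**Step 1: share unresolved at the last text, W = 10.**

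- Exponential: S(W) = 2^(−W/m). For m = 7, 2^(−10/7) = 0.371.
- Lognormal with log-SD s: S(W) = 1 − Φ((ln W − ln m)/s). For m = 7 and s = 0.5, (2.303 − 1.946)/0.5 = 0.713, so S = 0.238.

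| Assumed median (days) | Lognormal, s = 0.5 | Lognormal, s = 0.8 | Exponential |
|---|---|---|---|
| 5 | 8% (41 of 500) | 19% (97) | 25% (125) |
| 7 | 24% (119) | 33% (164) | 37% (186) |
| 10 | 50% (250) | 50% (250) | 50% (250) |
| 14 | 75% (375) | 66% (331) | 61% (305) |

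At a median of 10 days every shape gives 50%, by construction. Beyond that the survival curve does not fall to one half inside the window.

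**Step 2: what a later cap would leave unresolved.**

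| Assumed median (days) | Day 21: s = 0.5 / s = 0.8 / exponential | Day 28: s = 0.5 / s = 0.8 / exponential |
|---|---|---|
| 5 | 0.2% / 3.6% / 5.4% | 0.0% / 1.6% / 2.1% |
| 7 | 1.4% / 8.5% / 12.5% | 0.3% / 4.2% / 6.2% |
| 10 | 6.9% / 17.7% / 23.3% | 2.0% / 9.9% / 14.4% |
| 14 | 20.9% / 30.6% / 35.4% | 8.3% / 19.3% / 25.0% |

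Days are counted from first text. In every row a day-21 cap brings the unresolved share below one half, so the median becomes estimable.

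**Step 3: cost of ignoring the censoring** (lognormal, s = 0.5, one million simulated durations).

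| Assumed median (days) | True mean | Mean if the last text counts as recovery | Mean among resolved only |
|---|---|---|---|
| 7 | 7.9 | 7.0 | 6.1 |
| 10 | 11.3 | 8.5 | 7.0 |

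**Step 4: the start date.** Let L be the delay from diagnosis to platform entry; it is not stated, and 2, 4 and 7 days are assumed. Counted from diagnosis, texting lasts 10 − L = 8, 6 or 3 days and ends at day 10 after diagnosis. Counted from platform entry, it lasts 10 days and ends at day 10 + L = 12, 14 or 17 after diagnosis. The two readings give different amounts of data and different coverage of the late illness.

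**The case against.** The case for leaving the window alone has substance.

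- **The loss is partial.** A reader might infer that the late part of the illness is never observed. The documents do not support that. Anyone who resolves within the window and keeps replying has the end of the illness recorded. If the days run from platform entry, the recruitment delay moves the window towards the later illness. Only those unresolved at the last text are affected.
- **Return to work is not an endpoint.** A reader might infer that the study must supply return-to-work estimates. Section 1.1 names this only as background, as one use of simulations; sections 2.1, 4.1 and 4.4 do not mention it. The recovery-period wording is also background and can be read as meaning the same ten days. The point rests on sections 2.1, 4.1 and 4.4.
- **The stop rule is not selective.** A common stop day is administrative censoring, applied alike to everyone. Long episodes are the ones cut off, but the rule does not look at symptom state. The extension proposed below does.
- **The size is assumed.** Nothing in the documents shows that any symptom outlasts ten days in half of participants, and the share depends strongly on the distribution chosen. The counts out of 500 ignore the dropout that section 4.4 expects.
- **It is a descriptive pilot, and some aims need no longer follow-up.** Time-of-day variation and screening by symptoms or temperature can be studied within ten days.

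All of this stands as a limit on the claim. It does not remove the mismatch between a ten-day window and an objective and analysis plan that extend to the end of symptoms. Descriptive status explains why there is no power analysis; it does not make an unobserved duration observable.

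**Conclusion.** The point holds in a limited form. The fixed window right-censors fever and symptom duration for every participant unresolved at the last text, section 4.4 does not say how such episodes will be handled, and sections 1.1 and 4.3 disagree on when the ten days begin. The share affected cannot be derived from the documents. The illustrative range of 8% to 75% rests wholly on assumed medians of 5 to 14 days from first text, three assumed shapes and no dropout. The statement about medians is conditional: it applies only to a symptom that persists past the window in half or more of participants. This is a worthwhile, inexpensive improvement to the study's ability to answer its own question, not a flaw that invalidates what is collected within the ten days.

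**What to change.** 1. **Section 4.3, start date.** Define the start of the 10 days and reconcile it with section 1.1.
2. **Section 4.3, follow-up of those unresolved.** For anyone whose last available reply, whenever given, reports a symptom or fever, send automated texts once daily up to a pre-set cap such as day 21 or 28. At minimum, send one status text asking whether symptoms have ended and on what date. Using the last available reply keeps people who stopped answering before day 10 within the rule.
3. **Section 4.4, analysis.** Treat episodes unresolved at last contact as right-censored, using Kaplan-Meier or interval-censored estimates of duration. Report the percentage unresolved at day 10 and at the cap.
4. **If no extension is made.** Restate sections 2.1 and 4.1 as covering 10 days from the defined start. Item 3 still applies, with the day-10 percentage only.

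The extension costs a branching rule on the existing platform and a consent-form sentence on the longer maximum participation. Its downsides are a little more burden for those still symptomatic, further dropout after day 10, and relapses missed in participants who are not extended. A single status text is cheaper but relies on a recalled end date. Items 1, 3 and 4 cost only wording and a standard analysis.
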